## **1. INTRODUCTION**

Ocrelizumab (OCR), a humanized monoclonal antibody that selectively binds to and destroys CD20-expressing lymphocytes (B-cell lymphocytes), has demonstrated robust efficacy in reducing relapse rate, sustained disability worsening, and MRI indicators of disease activity in patients with relapsing multiple sclerosis (RMS). For patients with primary progressive MS (PPMS), OCR demonstrated reduction in disability progression compared to patients receiving the placebo treatment. The medication is well-tolerated with upper respiratory infections being the most common potential side effect followed by infusion-related reactions (IRRs). At least one infusion reaction occurred in 34.3% of the patients in OPERA I and OPERA II. The majority of the infusion reactions were mild to moderate and occurred with the first infusion of dose 1. In the clinical trials, all patients were pre-medicated with 100mg of methylprednisolone, and per the protocol, an analgesic/antipyretic such as acetaminophen and an IV or oral antihistamine such as diphenhydramine 50mg were recommended to use prior to starting OCR to minimize IRRs. However, drowsiness is commonly associated with diphenhydramine; therefore, a newer antihistamine such as cetirizine may be tolerated better without an increase in IRRs.

## **2. OBJECTIVES**

### **2.1 PRIMARY OBJECTIVE**

The primary objective of this pilot study is to evaluate whether there is some evidence that cetirizine is non-inferior to diphenhydramine in limiting the proportion and severity of reactions from OCR infusions.

### **2.2 SECONDARY OBJECTIVE**

The secondary objective of this study is to evaluate patient treatment satisfaction after receiving cetirizine and diphenhydramine as premedication for OCR infusions.

## **3. STUDY DESIGN**

### **3.1 DESCRIPTION OF THE STUDY**

This 6-month randomized controlled pilot study will determine whether there is some evidence that cetirizine is better tolerated than diphenhydramine without an increase in IRRs. Fifty-two patients, 26 patients per arm, will be randomized in a 1:1 ratio to receive cetirizine or diphenhydramine as premedication prior to OCR infusions on day 0 (1st half dose of 300mg), day 14 (2nd half dose of 300mg) and week 24 (1st full dose of 600mg). Neurological exams and the estimated Expanded Disability Status Scale (EDSS) will be obtained at screening and week 24, as well as premature termination visits, if applicable. Stanford Sleepiness Scale (SSS), and the Visual Analog Scale – Fatigue (VAS-F) will be administered at screening, baseline, day 14, and week 24. Modified Fatigue Impact Scale (MFIS) and Multiple Sclerosis Impact Scale (MSIS-29) will be administered at screening and week 24. MSIS-29 and MFIS will also be administered at premature termination, if applicable. Treatment Satisfaction Questionnaire for Medication (TSQM) will be administered at baseline, day 14, and week 24. TSQM, SSS, and VAS-F will be administered within 2 hours after each OCR infusion, followed by a phone call on the next business day following each infusion to collect and assess infusion reactions or other AEs.

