##### **4.5.1 Assessments during Treatment**

###### **Visit 1 or Screening Visit (-28 to -1 days prior to Baseline)**

- Informed consent
- Eligibility review
- Demographic information
- Review of disease and medical history
- Review of prior and concomitant medications, including lifetime MS disease modifying therapy history
- Reason(s) for switching to OCR
- Vital signs (blood pressure, heart rate, oral temperature, weight, and height)
- Neurological exam (may be historical exam if completed within 28 days prior to consent)
- Confirmation of estimated EDSS of 0 to 6.5, inclusive
- Laboratory assessments:
  - Urine or serum pregnancy test (females of childbearing potential only)
  - CBC and LFTs (may be historical laboratories if completed within 28 days prior to consent)
  - Hepatitis B testing (may be historical laboratories if completed within 6 months prior to consent)

- Serum immunoglobulins, quantitative (may be historical laboratories if completed within 28 days prior to consent)
- SSS
- VAS-F
- MFIS
- MSIS-29
- Adverse events

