#### **Visit 2 or Baseline Visit (Day 0)**

- Concomitant medications and adverse events
- Eligibility review (can be done day -7 to day 0)
- Randomization for premedication arm (can be done day -7 to day 0)
- Administration of premedication and OCR (300mg)
- Infusion reaction assessment
- TSMQ (Administered within 2 hours after OCR infusion, may be completed via phone)
- SSS (Administered within 2 hours after OCR infusion, may be completed via phone)
- VAS-F (Administered within 2 hours after OCR infusion, may be completed via phone)
- Phone Call (next business day) to assess infusion reactions and any other AEs

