#### **Visit 3 (Day 14 +/- 2 days from baseline)**

- Concomitant medications and adverse events
- Administration of premedication and OCR (300mg)
- Infusion reaction assessment
- TSMQ (Administered within 2 hours after OCR infusion, may be completed via phone)
- SSS (Administered within 2 hours after OCR infusion, may be completed via phone)
- VAS-F (Administered within 2 hours after OCR infusion, may be completed via phone)
- Phone Call (next business day) to assess infusion reactions and any other AEs

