#### **Visit 4 (24 weeks +/- 14 days from baseline)**

- Vital signs (blood pressure, heart rate, oral temperature, and weight)
- Neurological exam (must be completed pre-OCR infusion)
- Estimated EDSS (must be completed pre-OCR infusion)
- Concomitant medications and adverse events (AE reporting period continues 30 days following the last administration of study treatment or study discontinuation/termination, whichever is earlier. Reassess AEs via phone call at 30 days +7 from time of last dose or study termination.)
- Laboratory assessments:
  - Urine pregnancy test (females of childbearing potential only, if positive, confirm by serum pregnancy test)
  - CBC and LFTs
  - Serum immunoglobulins, quantitative
- Administration of premedication and OCR (600mg)
- Infusion reaction assessment

- TSMQ (Administered within 2 hours after OCR infusion, may be completed via phone)
- SSS (Administered within 2 hours after OCR infusion, may be completed via phone)
- VAS-F (Administered within 2 hours after OCR infusion, may be completed via phone)
- MFIS
- MSIS-29
- Phone call (next business day) to assess infusion reactions and any other AEs

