## APPENDIX A: STUDY FLOWCHART

Procedure/Visit	Visit 1 Screening (day -28 to -1)	Visit 2 Baseline (day 0)	Visit 3 (day 14±2 days)	Visit 4 (week 24±14 days)	Premature Termination Visit
Informed consent	X				
Eligibility review (INC/EXC)	X	X I			
Randomization		X I			
Demographics	X				
Vitals D	X			X	X
Disease & medical history	X				
Reason(s) for switching to OCR	X				
Neurological exam	X E			X K	X
EDSS (estimated)	X			X K	X
CBC & LFTs	X E			X	X
Serum immunoglobulins, quantitative	X E			X	X
Urine or serum pregnancy test F	X			X	
Hepatitis B testing	X G				
Premedication		X	X	X	
OCR infusion H		X	X	X	
Infusion reaction assessment		X	X	X	
Phone call		X B	X B	X B, J	X J
TSMQ		X A	X A	X A	
MFIS & MSIS-29	X			X	X
VAS-F	X	X A	X A	X A	
SSS	X	X A	X A	X A	
AEs	X	X	X	X	X
Con meds	X C	X	X	X	X
Primary reason for discontinuation					X

A: Administered within 2 hours post OCR infusion, may be completed via phone.

B: On next business day after OCR infusion to assess infusion reactions and any other AEs.

C: Prior & concomitant medications, including lifetime MS disease modifying therapy history.

D: To include heart rate, blood pressure, oral temperature, and weight. At screening only, also collect height.

E: May be historical if completed within 28 days prior to consent.

F: Females of childbearing potential only. Urine or serum test at screening. Urine test at week 24. If positive urine test, confirm by serum pregnancy test.

G: May be historical if completed within 6 months prior to consent.

H: 300mg IV at Visits 2 and 3, 600mg IV at Visit 4.

I: Can be done day -7 to day 0.

J: AE reporting period continues 30 days following the last administration of study treatment or study discontinuation/termination, whichever is earlier.

Reassess AEs via phone call at 30 days +7 from time of last dose or study termination.

K: Must be completed pre-OCR infusion.

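### SSS and VAS-F have no pre-dose reading on any infusion day and are compared unadjusted, which costs precision but does not bias the comparison of arms

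*Combined protocol and SAP*

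**What the plan says.** Section 3.1 gives the schedule for the two scales: "Stanford Sleepiness Scale (SSS), and the Visual Analog Scale – Fatigue (VAS-F) will be administered at screening, baseline, day 14, and week 24". A few sentences later it fixes the timing on infusion days: "TSQM, SSS, and VAS-F will be administered within 2 hours after each OCR infusion".

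The visit lists in section 4.5.1 agree. Visit 2, which is named the Baseline Visit, has one SSS entry: "SSS (Administered within 2 hours after OCR infusion, may be completed via phone". Visit 3 has one VAS-F entry: "VAS-F (Administered within 2 hours after OCR infusion, may be completed via phone". Visit 4 has the same pair of post-infusion entries. In Appendix A all three infusion-day cells for SSS and VAS-F carry the footnote "A: Administered within 2 hours post OCR infusion, may be completed via phone". Where the protocol wants a reading before the infusion it says so, as at week 24: "Estimated EDSS (must be completed pre-OCR infusion". SSS and VAS-F have no such instruction.

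The only score before any study drug comes from "Visit 1 or Screening Visit (-28 to -1 days prior to Baseline".

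Section 3.3.2 defines the endpoints as the scores after each infusion. Section 4.9.3(b) compares them between arms with Wilcoxon rank sum tests and no covariate. The same paragraph analyses MFIS and MSIS-29 by ANCOVA on the screening score. No use of the screening SSS and VAS-F scores in the between-arm test is stated.

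**The concern.** The trial exists because of drowsiness. Section 3.2 reports strong sedation with diphenhydramine, and drowsiness that remained a problem after its dose was lowered. Section 3.1 sets out to learn whether cetirizine is better tolerated. SSS and VAS-F are the scales that measure this directly.

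Patients with MS may arrive already tired. Without a reading on arrival, differences between patients in tiredness before dosing stay in the error term of each comparison. With 26 per arm, a real difference in sedation is then easier to miss, and a chance imbalance in tiredness on arrival can be neither seen nor corrected. Nor can the report describe how far a patient's score moved between arrival and the end of the infusion.

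**Working it through.** **The plan's own figure.** The only calculated sample size (section 4.9.6) is for the day-0 infusion-reaction endpoint: 25% in each arm, margin 0.30, one-sided 0.05, 80% power.

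n per arm = (1.645 + 0.842)² × 2 × 0.25 × 0.75 / 0.30² = 25.76, rounded up to 26. The stated figure reproduces. No size is calculated for SSS or VAS-F.

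**Age of the screening score at each infusion.** Inputs: screening 1-28 days before day 0; "Visit 3 (Day 14 +/- 2 days from baseline"; week 24 (day 168) ± 14 days.

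- Day 0: 1 to 28 days.
- Day 14: 12 + 1 = 13 days to 16 + 28 = 44 days.
- Week 24: 154 + 1 = 155 days to 182 + 28 = 210 days.

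**Is the planned contrast biased?** Assignment is 1:1 in permuted blocks of four (section 4.2), and both arms receive the same acetaminophen, methylprednisolone and OCR (sections 3.4 and 4.3.1). Tiredness on arrival is therefore balanced in expectation. A simulation of 5,000 trials per setting (26 per arm, normal scores, pre/post correlation 0.3 or 0.7) agrees. For a true difference of 0.50 SD the mean unadjusted estimate was 0.50 SD. With no difference, the Wilcoxon test rejected in 4.9% and 5.3% of trials.

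**What precision is lost?** The documents give no SD, effect size or correlation for these scales, so the results are in SD units and the correlation ρ is an assumption.

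- Unadjusted, two-sided 5%, 80% power: (1.960 + 0.842) × √(2/26) = 0.78 SD. For the Wilcoxon test with normal data, dividing by √(3/π) gives about 0.80 SD.
- Adjusted for a score with correlation ρ: 0.777 × √(1 − ρ²).

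| ρ | Error variance removed (ρ²) | Detectable difference | Power for 0.5 SD |
|---|---|---|---|
| none | 0% | 0.78 SD | 44% |
| 0.3 | 9% | 0.74 SD | 47% |
| 0.5 | 25% | 0.67 SD | 55% |
| 0.7 | 49% | 0.55 SD | 71% |

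Power is from the normal approximation. In the simulation, for a 0.5 SD difference, the unadjusted Wilcoxon test had about 40% power, and ANCOVA had 46% at ρ = 0.3 and 69% at ρ = 0.7.

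**How much needs a new reading?** Only the part beyond what the screening score would give. If, for illustration, screening correlates at 0.5 and a same-day score at 0.6, the detectable difference moves from 0.67 SD to 0.777 × √(1 − 0.36) = 0.62 SD.

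**The case against.** The best defence is that the endpoint is the post-infusion score and the question is which arm is sleepier. Randomisation answers that without a pre-dose score. This stands.

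Three stronger inferences are tempting, and the documents do not support them.

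- A reader might infer that drug sedation cannot be told apart from that day's MS fatigue, so that the comparison is confounded. It is not: such fatigue falls equally on both arms in expectation, and the unadjusted test holds its error rate.
- A reader might infer that the word baseline in section 3.1 contradicts a post-infusion reading. Baseline is the name of Visit 2, and section 3.1 itself states the post-infusion timing, in agreement with section 4.5.1 and Appendix A.
- A reader might expect a pre-dose score to show which patients were sedated by the antihistamine. It would remove tiredness present on arrival, but a rise after that still mixes the antihistamine with OCR and the background drugs. Section 3.4 also lists fatigue among the symptoms of an infusion reaction. No planned analysis classifies individual patients.

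Two further objections hold in part. The gain rests on correlations that the documents do not give, and it is small at 0.3. Also, randomisation may take place up to 7 days before day 0 and no blinding is described, so a self-report on arrival can be coloured by knowledge of the arm. At day 14 and week 24 it also follows experience of the assigned drug. This affects how the score should be used, but is no reason not to collect it.

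**Conclusion.** The gap is real and its consequence is modest. No SSS or VAS-F score precedes premedication on any infusion day, and the screening score is left out of the tests. The between-arm estimates remain unbiased. The cost is precision, protection against chance imbalance, and any account of within-patient change on the day.

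Under assumed correlations of 0.3 to 0.7, adjustment would lower the detectable difference from about 0.78 SD to between 0.74 and 0.55 SD. This assumes 26 evaluable patients per arm and roughly normal scores. Withdrawn patients are not replaced (section 4.5.1), so week 24 may have fewer. Even with adjustment, power for a 0.5 SD difference stays below 80% across this range.

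SSS and VAS-F are secondary outcomes in a pilot, and the stated secondary objective (section 2.2) is treatment satisfaction. This is a cheap improvement and does not threaten the primary conclusion.

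**What to change.** 1. Add SSS and VAS-F on arrival, before premedication, at Visits 2, 3 and 4. On day 0, take them before the patient is told the arm where possible. Update section 3.1, the visit lists in section 4.5.1 and the Appendix A footnotes.
2. In section 4.9.3(b), compare the post-infusion scores adjusted for a pre-dose score. Rank-based ANCOVA would keep the nonparametric approach.
3. State in advance which pre-dose score is used. One choice is the day-0 score at all three infusions. It precedes all study drug, but at week 24 it is as distant as the visit window makes it. The other is that day's own score, with a sensitivity analysis adjusting for the screening score, because later arrival scores are post-randomisation in a trial with no described blinding.
4. If no reading is added, at least adjust SSS and VAS-F for the screening score already collected, as the plan does for MFIS and MSIS-29. This needs one sentence and no new data.

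The cost is two short self-reports at visits that already take place, a few minutes of patient time at each, and small edits to the flowchart and the analysis section. The primary endpoint and the 26 patients per arm do not change.

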### **3.2 RATIONALE FOR STUDY DESIGN**

Shortly after the approval of OCR, we followed the premedication protocol used in OPERA I and II which included 100mg of methylprednisolone, 1 gram of acetaminophen, and 50mg of IV diphenhydramine. However, many patients experienced extreme sedation which caused severe drowsiness and impaired their ability to function, drive, or work during and after the infusion, and even the following day. As a result, we have decreased the dose of diphenhydramine to 25mg administered either IV or orally which has resulted in less, but still marked, drowsiness. Newer antihistamines such as cetirizine may be better tolerated; however, there is no evidence that they will be as effective in minimizing infusion reactions.

### **3.3 OUTCOME MEASURES**

#### **3.3.1 Primary Outcome Measure**

The proportion of patients having an infusion-related reaction, as defined by the Common Terminology Criteria (CTCAE), version 4 during or after the first-half dose of the first infusion on day 0. Infusion-related reactions will be documented at the infusion clinic on the day of the infusion and reported by the patient at the follow-up phone call the next business day after the infusion.

#### **3.3.2 Secondary Outcome Measures**

The proportion of patients having an infusion-related reaction during or after receiving the second half dose infusion on day 14.

The proportion of patients having an infusion-related reaction during or after receiving the first full 600mg dose infusion on week 24.

TSQM (Treatment Satisfaction Questionnaire for Medication) score after the infusions on day 0, day 14, and week 24.

SSS (Stanford Sleepiness Scale) score after the infusions on day 0, day 14, and week 24.

VAS-F (Visual Analog Scale for Fatigue) score after the infusions on day 0, day 14, and week 24.

MFIS (Modified Fatigue Impact Scale) score at week 24.

Physical and psychological MSIS-29 (Multiple Sclerosis Impact Scale) scores at week 24.

### **3.4 SAFETY PLAN**

Patients will be evaluated by a clinician at the start of the study and at week 24 prior to the 600mg OCR infusion. Phone visits will be conducted after each infusion (see Section 4.5, Study Assessments, and Appendix A, Study Flowchart).

A full neurological examination will be conducted at screening and week 24. Any worsening or new abnormality (including laboratory results) that is determined by the investigator as clinically significant will be recorded as an AE and will be monitored until resolution or stabilization. MS related symptoms are not to be reported as AEs unless,

in the opinion of the investigator, the symptoms are unusually serious and relevant.

The recommendation from the OCR prescribing information dated 12/2020^4 is to pre-medicate with 100mg of methylprednisolone (or an equivalent corticosteroid) administered 30 minutes prior to each OCR infusion to reduce the frequency and severity of infusion-related reactions (IRRs) [see Warnings and Precautions (5.1) in prescribing information].

For this study, all patients will receive 1,000mg of acetaminophen orally and 100mg of methylprednisolone via IV 30-60 minutes prior to each infusion. Additionally, patients will be randomized to receive either diphenhydramine 25mg orally or cetirizine 10mg orally 30-60 minutes prior to each OCR infusion to further reduce the frequency and severity of infusion reactions.

Recommended medications to be available if there is an infusion reaction (per treating investigator discretion):

- A. Epinephrine – anaphylaxis
- B. Albuterol – bronchospasm or hypoxia
- C. Famotidine 20mg IV – hives, itching, or anaphylaxis
- D. Oxygen therapy – shortness of breath, chest pain, or hypoxia
- E. Acetaminophen – pain, fever, and headaches
- F. Methylprednisolone – hives, itching, shortness of breath, or anaphylaxis

#### Suggested Management of IRRs

All CD20+ depleting agents administered via the intravenous route, including OCR, have been associated with acute IRRs. Symptoms of IRRs may occur during any ocrelizumab infusion, but have been more frequently reported during the first infusion. Physicians should alert patients that IRRs can occur within 24 hours of the infusion. These reactions may present as pruritus, rash, urticaria, erythema, throat irritation, oropharyngeal pain, dyspnea, pharyngeal or laryngeal edema, flushing, hypotension, pyrexia, fatigue, headache, dizziness, nausea, and tachycardia.

Patients should be observed for at least one hour after the completion of the infusion for any symptom of IRR. They will be informed about the possibility of delayed post-infusion symptoms and instructed to contact their study physician if they develop such symptoms.

Hypotension, as a symptom of IRR, may occur during ocrelizumab infusions. Therefore, withholding of antihypertensive treatments should be considered for 12 hours prior to and throughout each ocrelizumab infusion.

#### Severe IRRs

If a patient experiences a severe IRR or a complex of flushing, fever, and throat pain symptoms, the infusion should be interrupted immediately and the patient should receive symptomatic treatment. The infusion should be re-started only after all symptoms have resolved. The initial infusion rate at restart should be half of the infusion rate at the time of onset of the reaction.

#### Mild-Moderate IRRs

If the event that a patient experiences is a mild to moderate IRR (e.g. headache), the infusion rate should be reduced to half the rate at the time of the event. This reduced

rate should be maintained for at least 30 minutes. If tolerated, the infusion rate may then be increased according to the patient's initial infusion schedule.

See Section 5.1, Assessment of Safety, for complete details of the safety evaluation for this study.

### **3.5 COMPLIANCE WITH LAWS AND REGULATIONS**

This study will be conducted in accordance with current ICH GCP Guidelines and the Code of Federal Regulations for clinical research, applicable national and local health authorities, and IRB requirements. Any amendment to the study protocol must be approved by Providence IRB before implementation. AEs and protocol deviations must be reported according to the guideline of the IRB.

## **4.0 MATERIALS AND METHODS**

### **4.1 PATIENTS**

#### **4.1.1 Patient Selection**

Patient selection will be based on meeting all of the required inclusion and exclusion criteria to be eligible to participate in the trial.

#### **4.1.2 Inclusion Criteria**

1. Male or female patient with relapsing or progressive forms of MS, age 18 to 70 inclusive at the time of consent.
2. Able to understand the purpose, responsibilities and risks of the study and provide signed informed consent.
3. Naïve to OCR and will receive OCR as part of standard of care for MS treatment.
4. No evidence, in the opinion of the investigators of significant cognitive limitation or psychiatric disorder that would interfere with the conduct of the study.
5. Estimated EDSS of  $\leq 6.5$  at screening.
6. Female patients of childbearing potential must practice effective contraception and continue contraception during the study.

